### **6.11.2. Analyses of Multiplicity Adjusted Objectives**

[figure not shown]
A graphical approach for multiple comparisons (Bretz et al. 2011) will be used to strongly control the overall Type I error (2-sided alpha level of 0.05) for testing the treatment effect for the primary and the following multiplicity adjusted objectives: superiority of LY900014 compared with insulin lispro for (H2) 1-hour postprandial plasma glucose (PPG) excursion at the study primary endpoint, (H3) 2-hour PPG excursion at the study primary endpoint, and (H4) change from baseline to the study primary endpoint in HbA1c.

The graphical testing scheme for this study is displayed in [Figure 6.1](#). All the hypotheses are connected by lines with arrowheads indicating the directions of testing paths. The initial allocation of study total alpha for each hypothesis is located within the same node of the hypothesis. In this study, the study total alpha level (0.05) will be all used for the primary objective (H1) in the initial step. Then, the study total alpha level (0.05) will be allocated to other objectives according to the values of transition weights shown above the connecting lines in the figure once H1 is met. If 1 of the remaining objectives is successfully demonstrated with the given alpha level, its alpha will be allocated to the rest of objectives by the transition weights in the paths. The iterative test procedure continues until none of the remaining objectives can be demonstrated with their preserved alphas or all objectives are demonstrated successful.

An ANCOVA model with strata (country, type of basal insulin during the lead-in period, number of prandial doses at study entry, and HbA1c stratum) and treatment as fixed effects and baseline as a covariate will be used to analyze the 1-hour and 2-hour PPG excursions for all the

randomized subjects with data collected prior to discontinuation of IP. However, if the percentage of the patients with missing MMTT data at baseline is higher than 15%, a constrained longitudinal data analysis model (Liu et al. 2009; Lu 2010) will be used instead.

The superiority testing on change from baseline to the study primary endpoint in HbA1c will be assessed by the same analysis used for the primary objective. The analyses are described in Section 6.11.1. If the p-value is less than the alpha level allocated by the graphical approach, the superiority of LY900014 to insulin lispro will be achieved.

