10.3.3.2. Secondary Analyses

A graphical approach for multiple comparisons will be used to strongly control the overall Type I error (2-sided alpha level of 0.05) for testing the treatment effect for the primary and the following multiplicity adjusted objectives: superiority of LY900014 compared with insulin lispro for 1-hour PPG excursion at Week 26, 2-hour PPG excursion at Week 26, and change from baseline to Week 26 in HbA1c. The graphical testing scheme will be described in the SAP.

An ANCOVA model with strata (country, type of basal insulin, number of prandial doses at entry, and baseline HbA1c [$\leq 8.5\%$, $> 8.5\%$]), and treatment as fixed effects and baseline as a covariate will be used to analyze the 1-hour and 2-hour PPG excursions. However, if the percentage of the patients with missing MMTT data at baseline is higher than 15%, a constrained longitudinal data analysis model (Liu et al. 2009; Lu 2010) will be used instead. Analyses details will be documented in the SAP.

Superiority in change from baseline in HbA1c for LY900014 compared with insulin lispro will be determined from the analysis approaches outlined in Section 10.3.3.1.

Hemoglobin A1c and change from baseline in HbA1c at all time points will be analyzed by the same MMRM model used for the primary analysis..

Additional continuous secondary efficacy variables, as well as the change from baseline for these variables, will be analyzed either by the MMRM or ANCOVA models described in Section 10.3.1.

Treatment comparisons for the proportion of patients with HbA1c $< 7.0\%$ and $\leq 6.5\%$ will be analyzed using a longitudinal logistic regression with repeated measurements conducted by a generalized linear mixed model including independent variables of treatment, baseline HbA1c value, visit, baseline HbA1c by visit interaction, and treatment by visit interaction. An unstructured covariance structure will be used. As a sensitivity analysis, the proportion of patients with HbA1c $< 7.0\%$ and $\leq 6.5\%$ at Week 26 (Visit 18), imputed using LOCF, will be compared using a logistic regression model including treatment and baseline HbA1c value in the model.

Actual and change from baseline in basal, prandial, and total dose, as well as the prandial/total insulin dose ratio, will be analyzed by the MMRM models described in Section 10.3.1.

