**Table 6.2. Baseline and Post-Baseline Definitions and Patient Population by Study Period and Type of Analysis**

Study Period/Analysis	Patient Population	Baseline Observations	Post-Baseline Observations
Lead-In Period			
TEAEs	All Enrolled Patients	Prior to first dose of open-label insulin lispro (or Visit 2 date if the dose date is missing)	The entire lead-in period after first dose of open-label insulin lispro and prior to the first dose of IP (or Visit 8 date if the dose date is missing).
Basal, prandial, and total insulin doses, and prandial/total insulin dose ratios continuous analysis	All Randomized Patients	Visit 2	Visits 3 to 8 prior to initiation of IP
Weight MMRM and ANCOVA	All Randomized Patients	Last of Visits 1-2	Visits 3–8 AND Last of Visits 3-8
26-Week Treatment Period (including Safety Follow-Up Visit where applicable)			
HbA1c MMRM and ANCOVA	All Randomized Patients with a baseline and at least 1 post-baseline observation while on IP	Last of Visits 7-8	Visits 11, 13, 15, and 18 prior to discontinuation of IP AND Last of Visits 9-18 prior to discontinuation of IP
HbA1c categorical analyses longitudinal logistic regression and LOCF logistic regression	All Randomized Patients with a baseline and at least one post-baseline observation while on IP	Last of Visits 7-8	Visits 11, 13, 15, and 18 prior to discontinuation of IP AND Last of Visits 9-18 prior to discontinuation of IP
1-hr and 2-hr PPG and other MMTT variables	All Randomized Patients with a post-baseline observation while on IP	Visit 8 prior to initiation of IP	Visit 18 prior to discontinuation of IP
10-point SMBG, basal, prandial insulin doses, prandial/total insulin dose ratios	All Randomized Patients with a baseline and at least one post-baseline observation	Visit 8 prior to initiation of IP	Visits , 15, and 18 prior to discontinuation of IP AND Last of Visits 9-18 prior to discontinuation of IP

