### **6.3. Handling of Dropouts or Missing Data**

The analyses for the primary and multiplicity adjusted objectives will be performed with MMRM analysis including all data collected prior to permanent discontinuation of IP through Week 26.

Missing data will be addressed by using a mixed-effect model repeated measures (MMRM) analysis for continuous longitudinal variables. The MMRM model provides consistent estimator when data is missing at random. The model implicitly adjusts for missing data through a variance-covariance structure. An ANCOVA model will also be used to analyze continuous variables. Unless otherwise stated, missing endpoints will be imputed using the last-observation carried forward (LOCF) approach, using only postbaseline data, in the ANCOVA model.

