### 6.11.4. Sensitivity Analyses for Missing Data

No sensitivity analysis for missing data will be executed.

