### 7.1. Patients' Study Visits Impacted by COVID-19

Percentage and count of randomized participants with study visits impacted by COVID-19 will be compared by treatment groups. These participants includes, but not limited to six kinds, patients with any visit not performed, patients with any on-site visit changed to remote, patients with HbA1C missing, patients with 1,5 AG result missing, patients with MMTT result missing and patients with direct to patient drug supply. Listing of patients with study visits impacted by COVID-19 will also be provided.

For each of the six situations, a separate summary table and listing will be provided.

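### For the 1-hour and 2-hour PPG tests, use the already planned cLDA model throughout, not only when more than 15% of baseline MMTT data are missing (minor; a near-free gain in precision)

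*SAP*

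**What the plan says.** H2 and H3 are superiority tests inside the alpha-controlled graph; they can receive alpha once HbA1c non-inferiority is met. SAP 6.11.2 gives their model: strata and "treatment as fixed effects and baseline as a covariate will be used to analyze the 1-hour and 2-hour PPG excursions". The exception follows: "if the percentage of the patients with missing MMTT data at baseline is higher than 15" percent, "a constrained longitudinal data analysis model (Liu et al. 2009; Lu 2010) will be used instead". Protocol 10.3.3.2 carries the same rule, and so does the protocol synopsis.

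Three other places bear on it:

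- SAP Table 6.2 defines the population for PPG and other MMTT variables as "All Randomized Patients with a post-baseline observation while on IP". The HbA1c rows of the same table ask for a baseline value as well as a post-baseline one.
- SAP 6.3 fills missing endpoints by LOCF, "using only postbaseline data, in the ANCOVA model". Nothing fills a missing baseline. The same section says that the primary and multiplicity-adjusted objectives are analysed by MMRM, which is not what SAP 6.11.2 says for PPG.
- SAP 6.11.4: "No sensitivity analysis for missing data will be executed".

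**The concern.** An ANCOVA with baseline as a covariate can use only patients who have that baseline. With no imputation rule, a patient with a valid Week 26 excursion on IP but no usable baseline excursion has nowhere to go unless the 15% trigger fires. The population table includes this patient, yet the model cannot. The plan already names a model that would keep the patient, but reserves it for the worst case.

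The trigger is also loosely specified. Its denominator is not given (all randomized patients, or those with a Week 26 MMTT). Nor is it stated whether missing data means the whole test or the particular sample that an endpoint needs. Near 15%, two analysts could choose different models.

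At stake is some precision for two confirmatory tests, and agreement between the stated population and the patients analysed.

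**Working it through.** **The plan's own figure.** The documents give no SD, effect size or power for PPG. The stated power is for HbA1c (SAP 5.2): margin 0.4, SD 1.1, 320 and 160 completers. SE = 1.1 × √(1/320 + 1/160) = 0.1065; 0.4/0.1065 − 1.960 = 1.796; power = Φ(1.796) = 96.4%, against 96% stated. For dropout, 480/0.85 = 564.7, against about 564 stated. Both reproduce. The 480 completers serve below as the number with a Week 26 MMTT.

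**Who can be lost.** Only patients with a Week 26 excursion have an outcome to lose. At the limit that is 0.15 × 480 = 72, leaving 408 in the ANCOVA.

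**Information.** Let m be the share without a baseline excursion (missing at random) and ρ the baseline-to-Week-26 correlation. In large samples, per patient with a Week 26 value:

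- ANCOVA on complete pairs: (1 − m)/(1 − ρ²)
- cLDA: (1 − m)/(1 − ρ²) + m
- Gain of cLDA over ANCOVA: m(1 − ρ²)/(1 − m)
- Share of full-data information kept: ANCOVA 1 − m; cLDA 1 − mρ²

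The documents give no ρ, so a range is assumed.

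| m | patients of 480 | gain, ρ = 0.7 | ρ = 0.5 | ρ = 0.3 |
|---|---|---|---|---|
| 2% | about 10 | 1.0% | 1.5% | 1.9% |
| 5% | 24 | 2.7% | 3.9% | 4.8% |
| 10% | 48 | 5.7% | 8.3% | 10.1% |
| 15% | 72 | 9.0% | 13.2% | 16.1% |

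Example at 15% and ρ = 0.7: 0.15 × 0.51/0.85 = 9.0%. At 15% ANCOVA keeps 85.0% of the full information; cLDA keeps 92.6%, 96.2% and 98.7% at ρ = 0.7, 0.5 and 0.3. The ANCOVA confidence interval is wider by 4.4%, 6.4% and 7.7%.

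**Power, from an assumed 80% with complete baselines.** Power = Φ(√I × (1.960 + 0.842) − 1.960), where I is the share kept. At 15% missing, ANCOVA: √0.85 × 2.802 − 1.960 = 0.623, so 73.3%. cLDA: 76.9% at ρ = 0.7, rising to 80.0% at ρ = 0. At 5% missing: ANCOVA 78.0%, cLDA 79.0% to 80.0%. At 1–2% missing the gap is under one point. From an assumed 90%, the 15% figures are 84.8% against 87.7% to 90.0%.

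**Simulation check** (480 patients, 2:1, one binary stratum, 400 runs per setting, cLDA by maximum likelihood). With complete baselines the two models gave the same estimate in every run, with SEs within 0.5%. At 15% missing, with a true effect set for about 80% power, rejection was 72.0% against 79.5% (ρ = 0.3), 74.8% against 78.8% (0.5) and 70.8% against 75.8% (0.7), ANCOVA first; this agrees with the formula within simulation error. Neither model showed material bias.

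**A condition on the equality.** It holds when the strata are interacted with visit. With strata as main effects only, cLDA forces one stratum effect on both visits. In checks with complete data and a stratum effect assumed to differ strongly between visits, the SE was about 8–9% larger than under ANCOVA.

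**The case against.** The strongest reply is that the problem should hardly arise. The protocol's Schedule of Activities (footnote c) holds randomization until the baseline MMTT is done. What remains is mainly a completed test with an unusable sample, and two fasting samples are planned (SAP 6.11.5 averages −15 and 0 minutes). This stands, and it is why the point is minor.

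The rule is also pre-specified in both documents, and ANCOVA is a valid model. A reader might infer that choosing the model after data are in makes the confirmatory test unsafe. The documents do not support that. The trigger rests on a test done before randomization in a double-blind trial, so it cannot depend on the assigned arm, and no Type I error inflation is shown.

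Other stronger readings also fail:

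- One might take 15% of 564 randomized patients, about 85, as the number of outcomes discarded. Patients without a Week 26 MMTT have none to discard, and protocol 9.1.4.3 does not perform the test after IP is stopped. The ceiling is about 72 of 480.
- SAP 7.1 plans to count "patients with MMTT result missing" because of COVID-19. It names no visit, so it is not evidence of missing baselines, and cLDA does not recover a missing Week 26 value.
- Table 6.2 might be called a flat contradiction. It names a population and not a model, its wording would suit the cLDA fallback, and the SAP nowhere says that these patients are excluded. Their exclusion is an inference from the model and the absence of a baseline imputation rule. The inference is sound, since the HbA1c rows do ask for a baseline. Protocol 10.3.1 requires a baseline only when the response is a change from baseline; H2 and H3 concern the Week 26 excursion itself.

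**Conclusion.** The point holds as a minor, nearly free improvement. At or below the trigger, the ANCOVA cannot analyse some patients whom Table 6.2 includes; the plan's own fallback can. The loss is one of precision: at most about 72 of 480 completers at the limit, with an information gain from cLDA of 1–2% at 2% missing, 3–5% at 5% and 9–16% at 15%. With the baseline test required before randomization, the low end is the more likely.

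These figures rest on an assumed correlation of 0.7 to 0.3, baselines missing at random, and 480 patients with a Week 26 MMTT. The power figures also assume a starting power, because the plan gives none for PPG; neither claim is shown to be at risk. The statement that cLDA costs no precision with complete baselines depends on the strata-by-visit terms.

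**What to change.** In SAP 6.11.2, protocol 10.3.3.2 and the protocol synopsis, remove the 15% trigger and make cLDA the single analysis for H2 and H3. Specify it fully:

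- baseline and Week 26 excursions as the two responses;
- a common baseline mean across arms, justified because the baseline MMTT precedes randomization and all patients receive insulin lispro at it (protocol 9.1.4.3);
- unstructured covariance;
- each stratification factor interacted with visit, so that the result matches ANCOVA when baselines are complete.

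Keep the ANCOVA as a supportive analysis. At the same time reconcile SAP 6.3, which says the multiplicity-adjusted objectives use MMRM, with the model in SAP 6.11.2.

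The cost is a wording change and a program that the fallback requires anyway. The downside is a slightly more complex model to explain.

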**Figure 6.1. Testing scheme for primary and multiplicity adjusted objectives.**

### 6.11.3. Additional Analyses of the Primary Outcome

The primary MMRM analysis model will be repeated using the PP and Completer populations as a sensitivity analysis. If the conclusion differs from that of all randomized patients, the data and analyses will be further investigated.

A secondary analysis model for the change from baseline to study primary endpoint in HbA1c will be an ANCOVA with strata (country, type of basal insulin during the lead-in period, and number of prandial doses at study entry) and treatment as fixed effects and baseline as a covariate. Missing endpoints will be imputed using the LOCF approach using post-baseline data only.

### 6.11.4. Sensitivity Analyses for Missing Data

No sensitivity analysis for missing data will be executed.

### 6.11.5. Other Secondary Efficacy Analyses

The analyses described in Section 6.11.5 to Section 6.11.6 will include data collected from all randomized patients prior to permanent discontinuation of IP. The longitudinal observations of actual and change from baseline in HbA1c up to Week 26 will be analyzed using the same MMRM model as for the analysis of the primary outcome. For the following secondary efficacy endpoints, an MMRM model similar to that for the primary outcome with an additional term of HbA1c stratum ( $\leq 8.5\%$ ,  $> 8.5\%$ ) will be used:

- actual and change from baseline 1,5-AG values
- actual and change from baseline 10-point SMBG values (fasting, 1 hour post morning meal, 2 hours post morning meal, pre midday meal, 1 hour post midday meal, 2 hours post midday meal, pre evening meal, 1 hour post evening meal, 2 hours post evening meal, and bedtime)
- actual and change from baseline in total, basal, and prandial insulin doses and prandial/total insulin dose ratios

Three 10-point SMBG profiles are expected to be collected during the 2 weeks prior to specified visits. Valid SMBG profiles will be used for analysis, defined as having non-missing values at  $\geq 6$  time points among the 10 pre-specified time points and being collected during 2 weeks prior to a given visit. For each time point, the average of the corresponding SMBG values from the valid SMBG profiles will be used for analysis. The excursion of SMBG for each meal category (that is, morning meal, midday meal, and evening meal) calculated using the average values at the corresponding time points will be used for analysis.

The following endpoints, collected from the MMTT, will be analyzed using the ANCOVA model with strata (country, type of basal insulin during the lead-in period, number of prandial doses at study entry, and HbA1c stratum) and treatment as fixed effects and baseline as a covariate:

- actual and change from baseline in fasting glucose (average of measurements at time -15 and 0), and PPG at 15, 30, 60, 120, 180, and 240 minutes after the meal
- PPG excursions at time 15, 30, 180, and 240 minutes after the meal (PPG minus fasting glucose)

Sensitivity analysis for PPG excursions may be performed to exclude patients whose PPG excursion could be affected by factors including MMTT consumption amount (for example, partial MMTT was consumed) and correction bolus insulin usage. A summary of the MMTT consumption and bolus insulin dose at baseline and Week 26 will be provided.

Treatment comparisons for the proportion of patients with HbA1c  $< 7.0\%$  and  $\leq 6.5\%$  will be analyzed using a longitudinal logistic regression with repeated measurements conducted by a generalized linear mixed model including independent variables of treatment, baseline HbA1c value, visit, baseline HbA1c-by-visit interaction, and treatment-by-visit interaction. An unstructured covariance structure will be used. As a sensitivity analysis, the proportion of patients with HbA1c  $< 7.0\%$  and  $\leq 6.5\%$  at Week 26 (Visit 18), imputed using LOCF, will be compared using a logistic regression model with terms for treatment and baseline HbA1c value.

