## 6.2. Adjustments for Covariates

Stratification factors of this study include country (China vs. Other), HbA1c stratum at baseline ( $\leq 8.5\%$  vs.  $>8.5\%$ ), type of basal insulin during the lead-in period (glargine U-100 vs. degludec U-100), and number of prandial doses at study entry ( $<3$  vs.  $\geq 3$ ).

For the primary analysis of HbA1c, the stratification factor of HbA1c stratum (baseline) will not be included. Instead, the continuous value of baseline (Visit 8) HbA1c will be included in the analysis models.

Other efficacy analyses and safety analysis will include the stratification factors as noted in Sections [6.11](#) and [6.12](#).

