## 6.11. Efficacy Analyses

### 6.11.1. Primary Outcome and Methodology

The primary objective of this study (H1) is to test the hypothesis that LY900014 is noninferior to insulin lispro on glycemic control (NIM=0.4% for HbA1c) in patients with T2D, when administered as prandial insulin (0 to 2 minutes prior to the meal), in combination with basal insulin for 26 weeks.

The primary efficacy comparison will be based on the contrast between LY900014 and insulin lispro at Week 26 (Visit 18) from the MMRM analysis of change from baseline in HbA1c including data collected from all randomized patients prior to permanent discontinuation of IP through Week 26. The model for the analysis of the primary efficacy endpoint of change from

baseline in HbA1c will include the fixed class effects of treatment, strata (country, type of basal insulin during the lead-in period, and number of prandial doses at study entry), visit, and treatment-by-visit interaction, as well as the continuous, fixed covariates of baseline value. An unstructured covariance structure will be used to model the within-patient errors. Significance tests will be based on LS means and Type III tests. If this analysis fails to converge, the following covariance structures will be tested in order:

- Toeplitz with heterogeneity
- autoregressive with heterogeneity
- compound symmetry with heterogeneous variances
- Toeplitz
- autoregressive
- compound symmetry without heterogeneous variances

The first covariance structure that converges will be used. The Kenward-Roger approximation will be used to estimate denominator degrees of freedom.

For both primary analysis approaches, LY900014 will be declared noninferior to insulin lispro if the upper limit of the 2-sided 95% CI for the LS mean difference in the change from baseline in HbA1c for LY900014 minus insulin lispro is below +0.4%.

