#### **6.11.6. Analyses of Exploratory Objectives**

For the Insulin Treatment Satisfaction Questionnaire (ITSQ), the change from baseline to LOCF endpoint while on treatment in each domain transformed score (inconvenience, lifestyle, hypoglycemic control, glycemic control, delivery system) and overall transformed score will be analyzed using the ANCOVA model with strata (country, type of basal insulin during lead-in

period, number of prandial doses at study entry, and HbA1c stratum), and treatment as fixed effects and baseline as a covariate.

Summary statistics, including number of patients and proportion of categorical outcomes (5 levels) for the 5 dimensions (mobility, self-care, usual activity, pain/discomfort, and anxiety/depression) of the European Quality of Life – 5 Dimensions 5 Level (EQ-5D-5L) will be provided by visit and by treatment. The change from baseline to LOCF endpoint (Week 26, Visit 18) in the EQ-5D-5L United Kingdom (UK) population-based health state index score and EuroQol visual analog scale (EQ-VAS) score will be analyzed using the ANCOVA model **CCI**

For the Work Productivity and Activity Impairment Questionnaire General Health (WPAI-GH), the change from baseline to LOCF endpoint in each score (absenteeism, presenteeism, work productivity loss, and activity impairment) will be analyzed using the ANCOVA model similar to ITSQ.

Within-day and between-day glycemic variability measured by the SD and the coefficient of variation (CV) of 10-point SMBG profiles will also be analyzed by MMRM model specified in Section 6.11.5. At a given visit, the CV and SD on each day with a valid SMBG profile will be calculated using all the glucose values within that day, then the average values of these CVs and SDs will be used as the within-day CV and SD at that visit in analysis. At a given visit, the CV and SD at each of the 10 pre-specified SMBG time points will be calculated using the corresponding glucose values of the valid SMBG profiles, then the average values of these CVs and SDs will be used as the between-day CV and SD at that visit in analysis. [Table 6.3](#) lists additional variables for potential exploratory analyses.

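### Both logistic models for the HbA1c targets leave out three randomization factors that every other SAP 6.11 efficacy model with readable terms includes

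*SAP*

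**What the plan says.** Protocol 7.2 and SAP 5.3 stratify randomization by four factors: country, HbA1c stratum, basal insulin type during lead-in, and number of prandial doses at entry.

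For the two HbA1c target endpoints, SAP 6.11.5 gives the longitudinal logistic model the "independent variables of treatment, baseline HbA1c value, visit, baseline HbA1c-by-visit interaction, and treatment-by-visit interaction". The LOCF sensitivity analysis is a "logistic regression model with terms for treatment and baseline HbA1c value". Protocol 10.3.3.2 lists the same terms for both.

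Elsewhere in SAP 6.11:

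- Primary HbA1c MMRM (6.11.1): "strata (country, type of basal insulin during the lead-in period, and number of prandial doses at study entry), visit, and treatment-by-visit interaction".
- 1-hour and 2-hour PPG excursions (6.11.2): "An ANCOVA model with strata (country, type of basal insulin during the lead-in period, number of prandial doses at study entry, and HbA1c stratum".
- HbA1c change with LOCF (6.11.3): "an ANCOVA with strata (country, type of basal insulin during the lead-in period, and number of prandial doses at study entry".
- 1,5-AG, SMBG and insulin doses (6.11.5): an "MMRM model similar to that for the primary outcome with an additional term of HbA1c stratum".
- Questionnaire ANCOVA (6.11.6), whose list of terms ends "period, number of prandial doses at study entry, and HbA1c stratum), and treatment as fixed effects and baseline as a covariate".

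On covariates in general, SAP 6.2 states: "Other efficacy analyses and safety analysis will include the stratification factors as noted in Sections" 6.11 and 6.12.

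**The concern.** The target endpoints dichotomize the same HbA1c values that the primary MMRM and the LOCF ANCOVA analyse as continuous, from the same visits and with the same cut at discontinuation of study drug (SAP Table 6.2). The continuous form is adjusted for the three design factors and the binary form is not. Neither document says why, and SAP 6.2 only points back to 6.11.

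Stratified randomization balances these factors between arms. If they are prognostic, a model that leaves them out does not credit that balance: its standard error is somewhat too large, the test is mildly conservative, and some power is lost. Bias is not at stake. An odds ratio that is smaller without the factors reflects non-collapsibility.

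**Working it through.** **The plan's own figure (background only).** SE = 1.1 × √(1/320 + 1/160) = 0.1065. Power = Φ(0.4/0.1065 − 1.96) = Φ(1.80) = 96.4%, against the stated 96%. With 15% dropout, 480/0.85 = 565, against the stated approximate 564. Both reproduce. The point here does not rest on them.

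**Inventory of SAP 6.11.**

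| Model | Country, basal type, doses |
|---|---|
| Primary MMRM; HbA1c superiority (same model) | included |
| PPG excursion ANCOVA | included |
| LOCF ANCOVA for HbA1c | included |
| MMRM for 1,5-AG, SMBG, doses | included |
| Other MMTT ANCOVA | included |
| ITSQ ANCOVA; WPAI-GH and glycemic variability by cross-reference | included |
| Longitudinal logistic, HbA1c targets | none |
| LOCF logistic, HbA1c targets | none |

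Three items cannot be classed from the SAP. The constrained longitudinal fallback and Table 6.3 list no terms, and the EQ-5D-5L model text is redacted (Protocol 10.3.5.1 sends it to the 10.3.1 ANCOVA, which has strata).

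**Size, by simulation.** For the LOCF form the two models compared are:

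- without: logit p = α + θ·treatment + β·baseline HbA1c
- with: the same + γ₁·country + γ₂·basal type + γ₃·doses

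The longitudinal form adds visit, treatment-by-visit and baseline-by-visit terms, an unstructured 4×4 covariance and the Week 26 contrast. It was fitted as a marginal (residual-side) model.

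- From the documents: 564 patients, 2:1 allocation, China share 450/564, 15% missing at Week 26, HbA1c at Visits 11, 13, 15 and 18.
- Assumed: permuted blocks of 6 in 16 strata; glargine 70%; ≥3 doses 50%; baseline HbA1c mean 8.2, SD 0.9; log-odds slope −1 per 1% HbA1c; treatment OR 1.75; control attainment 20% or 40%; one common OR for the three factors; random monotone dropout; within-patient correlation 0.55–0.80.
- 4,000 trials per cell; Monte Carlo SE of a type I error √(0.05 × 0.95/4000) = 0.003.

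Power (%) without → with the factors:

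| Factor OR | Longitudinal, 20% | Longitudinal, 40% | LOCF, 20% | LOCF, 40% |
|---|---|---|---|---|
| 1.3 | 61.6 → 62.1 | 76.3 → 76.7 | 63.6 → 64.3 | 77.4 → 77.8 |
| 1.65 | 60.9 → 61.9 | 74.3 → 75.4 | 62.5 → 63.5 | 75.9 → 77.0 |
| 2.0 | 60.8 → 62.3 | 72.4 → 74.1 | 62.4 → 64.2 | 73.2 → 75.6 |
| 2.72 | 57.9 → 61.5 | 68.9 → 72.8 | 59.6 → 63.8 | 69.9 → 74.1 |

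The differences, in points, are 0.4–0.5, 1.0–1.1, 1.5–1.7 and 3.6–3.9 for the longitudinal model, and 0.4–0.7, 1.0–1.1, 1.8–2.4 and 4.2 for LOCF.

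Type I error is 0.036–0.052 without the factors and 0.043–0.053 with them, so adding them shows no inflation.

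For the longitudinal model at factor OR 2.72:

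- Treatment OR is 1.65–1.69 without and 1.77–1.79 with the factors, but the standardized risk difference is the same: 8.4 vs 8.4 and 10.8 vs 10.8 points.
- Model SE divided by empirical SE is 1.051 and 1.046 without, 1.013 and 0.997 with.
- The empirical SD of the risk difference barely moves: 3.59 to 3.57 and 4.20 to 4.17 points. The power gain comes from a correct standard error, not from a more precise estimate.

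At 8% attainment, longitudinal power is 36.8 vs 36.8 (factor OR 1.3) and 32.9 vs 34.6 (OR 2.72).

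**Cross-checks on the single-visit logistic model (n=480).** With treatment log-OR 0.5 and 1,000 trials per cell, power without vs with the factors was 63% vs 64%, 59% vs 61% and 57% vs 62% at factor log-OR 0, 0.5 and 1.0. Rejection under no effect was 4.9%, 6.2% and 3.5% without, and 5.2%, 6.7% and 4.3% with (Monte Carlo SE 0.7 point). Another run gave losses of about 0.6 point at factor OR 1.3, 0.9–1.2 at 1.65 and 4.3–4.5 at 2.72, a standard error 2–5% too large without the factors at 2.72, and type I error 0.046–0.057 with them.

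**The case against.** The plan does what it says. SAP 6.2 does not promise strata in every model, and the protocol lists the same terms. Grouped by outcome type, the plan is uniform: Protocol 10.3.1 attaches strata to MMRM and ANCOVA for continuous variables, while the binary and count models with stated terms, including the hypoglycemia models in SAP Table 6.5, omit them. Continuous baseline HbA1c is already in both models and covers the fourth factor. Nothing in the documents shows that the other three are prognostic beyond it. A treatment OR of 1.75 is also generous in a trial designed on no true HbA1c difference. With sparse events the larger model is less stable.

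Most of this stands, and it sets the weight of the point. The models are valid, nothing is contradicted, and the larger losses need all three factors at OR 2.72 together. At factor OR 1.3 the type I errors with and without the factors are practically equal, so the conservatism depends on prognostic factors. The longitudinal figures cover only the marginal reading of the planned generalized linear mixed model; a version with patient random effects was not simulated.

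The grouping by outcome type describes the pattern but does not justify it. Analysing by the factors used to randomize costs almost nothing here, and no reason is given for treating the binary form of HbA1c differently from the continuous form.

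**Conclusion.** The concern holds as an optional improvement. Among efficacy models in SAP 6.11 with readable terms, only the two HbA1c target models omit the three factors. The expected cost ranges from about half a power point (each factor OR 1.3) to about 4 points (OR 2.72), and is close to zero if the factors add little to baseline HbA1c. The factor effects, treatment effect and attainment rates are all assumptions, because the documents give none. The standardized risk difference is unaffected. SAP 6.5 makes no multiplicity adjustment for these endpoints, so no confirmatory conclusion changes.

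**What to change.** In SAP 6.11.5, add country, basal insulin type during lead-in and number of prandial doses at entry as fixed effects to both logistic models, for both HbA1c thresholds. Keep continuous baseline HbA1c. Record the difference from Protocol 10.3.3.2 and its reason in the SAP, as SAP 6.1 allows, before unblinding.

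Section 6.11.5 gives no fallback if the unstructured covariance fails to converge. State that the covariance is then simplified in the order of 6.11.1 and that the three factors stay in the model. That order was written for the continuous MMRM, and model-based standard errors under the simpler structures were not simulated for the logistic model.

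The cost is wording only, since the factors are already collected for randomization. The larger longitudinal model failed to converge in 1 of 64,000 simulated trials at 20–40% attainment. At 8% attainment with factor OR 2.72 it failed in 0.3–1.2% (0–0.1% without the factors), and a few fits gave very large standard errors. If the sponsor prefers the smaller models, one sentence of rationale in 6.11.5 would explain the difference.
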